12.4 Analysis of Secondary Endpoints

Secondary (exploratory) endpoints (changes in sleep continuity (sleep efficiency, total sleep time, sleep latency), quality-of-life measures, depression, anxiety, and subjective cognitive function) will be analyzed by modified intention to treat. Since no pre-existing data describes the magnitude of associations of our exploratory outcomes with naltrexone use in this population, we are unable to speculate on the statistical power required to detect an effect. Any relevant associations and their statistical significances will be calculated using descriptive statistics. In addition, radiation therapy status (currently receiving RT vs. recently completed RT) will be included as a covariate in the multivariate analysis.

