Intervention phase: Radiation oncologists will consent patients who develop treatment-emergent fatigue developing during or within one month after completion of radiation therapy and who are interested in participating in the intervention phase of the study. After informed consent is obtained and final eligibility determination is complete, participants will have 5 study visits: one at study entry to initiate treatment (week 0), one to rule out any contraindication to the scheduled dose escalation (week 1), one at the conclusion of medication treatment for treatment outcome assessment and safety monitoring (week 5), and the last at four weeks after discontinuation of study drug vs. placebo (week 9). All intervention visits have a window of ± 7 days.

Study treatment: The treatment schedule includes a daily dose of double-blinded naltrexone vs. placebo for 5 weeks. Treatment will be initiated at 25 mg/day (or equivalent placebo) during the first week to improve tolerability. The dose will be escalated to 50 mg/day (or equivalent placebo) after one week barring significant early improvement in fatigue or adverse events precluding dose escalation, and participants will continue to take 50 mg/day (or 25 mg/day if dose is not escalated) for 4 weeks to complete a 5-week treatment period.

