2.3 Rationale

Radiation Therapy

The majority of cancer patients receiving radiation therapy are treated with fractionated external beam radiation, in which a daily dose of radiation from an external source targets a tumor within the body. A significant portion of patients receiving external beam radiation experience fatigue three to four weeks into a typical five- to eight-week radiation course, regardless of the location of the tumor or the radiation field. This fatigue usually lasts for approximately three weeks after treatment and either resolves spontaneously, or can persist for weeks to months.

Interestingly, patients receiving radiation that targets only superficial structures (i.e. breast cancer patients) can become equally as fatigued as patients receiving radiation to deeper structures, and fatigue is more highly correlated with skin dose and field size than with depth of radiation^{28,29}. In fact, the one commonality among radiation therapy regimens that cause fatigue is that there is a significant skin dose. This led us to hypothesize that factors produced in the skin in response to radiation may play a role in radiation-induced fatigue.

DNA damage resulting from radiation exposure causes upregulation of expression of p53 dependent genes in skin cells. One recently-identified p53-dependent gene upregulated in keratinocytes in response to radiation exposure encodes a long-lived endogenous opioid called β -

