endorphin³⁰. β -endorphin induction following radiation exposure was observed during studies elucidating the pathway through which ultraviolet radiation stimulates skin pigmentation (tanning). In the pigmentation response following ultraviolet radiation exposure, there is a p53-induced expression of pro-opiomelanocortin (POMC) in keratinocytes. POMC is cleaved into various biologically-functional peptides. One of these peptides, Melanocyte Stimulating Hormone (MSH), is important in the tanning response, acting in a paracrine fashion to stimulate melanocytes to produce pigment. Another peptide derived from POMC production and cleavage following multiple types of DNA damage is the endogenous opioid β -endorphin. Opioid drugs (such as morphine) often cause fatigue and lethargy when they are used to treat pain. [name] data in mice show that plasma β -endorphin levels are elevated significantly by 3 weeks into a 6-week regimen of daily tail radiation that models radiation therapy in cancer patients receiving radiation to superficial structures. In contrast to humans, mice do not exhibit fatigue in response to exogenous administration of opiate drugs³¹. However, quantitative behavioral studies indicated significant changes in phenotypes associated with morphine administration, including mechanical and thermal nociception, in tail-irradiated mice that did not occur in non-irradiated mock-treated counterparts. Furthermore, these changes were reversed upon administration of the opioid antagonist naloxone. In these tail-irradiated mice, β -endorphin plasma levels diminish over the 4 weeks following the end of the radiation regimen.

Chemotherapy

Patients receiving chemotherapy typically become debilitatingly fatigued, even more predictably than radiation therapy patients. As mentioned above, the increased production of β -endorphin following radiation exposure-induced DNA damage is a p53-dependent process. Many common chemotherapeutics are DNA damaging agents that induce p53, and therefore p53-dependent genes, to cause apoptosis of cancer cells³². As transcription of the gene encoding β -endorphin is responsive to p53, it is thus plausible that the fatigue caused in patients receiving chemotherapy is the result of increased β -endorphin production following chemotherapy-induced p53 up-regulation in target cells. A treatment that blocked the effects of β -endorphin might then also reduce any residual fatigue from chemotherapy.

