12. STATISTICAL CONSIDERATIONS

Entry criteria of a drop of 10 points on FACIT-fatigue subscale was selected because a change of 10 points has been shown to constitute a clinically meaningful difference on this subscale⁵³. The effect of naltrexone (and placebo in the control group) will be defined as a difference (in raw FACIT score) between the pre-randomization FACIT and the follow-up FACIT. FACIT-fatigue subscale scores are normally distributed in anemic and nonanemic cancer populations⁴², with a standard deviation of 10 points. Setting power as 0.8, and significance as 0.05, assuming a two-sided type I error, 122 patients per arm are required to detect a “difference of a difference” of at least 3.6 points on FACIT-fatigue. The 3.6 point difference was selected because it is the approximate mean of prior effect sizes utilizing FACIT-fatigue in clinical trials of erythropoietin or darbopoeitin vs. placebo. Assuming a 20% drop-out rate, approximately 150 patients per arm will be randomized.

An interim analysis will be conducted on one occasion, after collecting data for the first 75 patients in each arm. This analysis will be conducted in light of several possibilities: 1) the observed benefit of naltrexone is so promising that it would be unethical not to use it for all eligible patients, 2) the observed rate of side effects/toxicity is too high, 3) futility –it appears to be unlikely that there is a clinically significant difference between the naltrexone and placebo arms. The Haybittle–Peto boundary rule (with 0.001 significance threshold) will be employed to determine whether the trial should be stopped early. The final analysis will still use the 0.05 threshold of significance.

Futility testing will also be performed on the primary outcome at a low level (one-sided alpha 0.0025) on one occasion (after the first 75 patients are enrolled).

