12.3 Stratification Factors

Patients will be stratified according to whether or not they received chemotherapy.

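### Radiotherapy status at randomisation is a plausible prognostic factor, but the plan names it as a covariate only under the secondary endpoints; it should be written into the primary FACIT-F model

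*Combined protocol and SAP*

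**What the plan says.** **Entry window.** Section 1.1 admits patients to the intervention phase with fatigue "developing during or within one month after completion of radiation therapy". The randomised group therefore mixes patients still being irradiated with patients who have finished.

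**Course of fatigue.** Section 2.1 reports that fatigue builds gradually over a course of breast RT. Section 2.2 says it improves on its own afterwards, with most patients back at pre-treatment levels by three months, and gives spontaneous recovery as a reason for the five-week treatment period. Section 2.3 adds: "This fatigue usually lasts for approximately three weeks after treatment and either resolves spontaneously, or can persist for weeks to months".

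**Primary comparison.** Sections 10, 12 and 12.1 define the effect as the raw FACIT difference between the score before randomisation and the follow-up score. They name no test, model or covariate.

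**RT status.** It appears as an analysis covariate once, in the last sentence of Section 12.4 (Analysis of Secondary Endpoints): "radiation therapy status (currently receiving RT vs. recently completed RT) will be included as a covariate in the multivariate analysis". That multivariate analysis is not described anywhere.

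**Randomisation.** Section 12.3 states: "Patients will be stratified according to whether or not they received chemotherapy". Section 4.3 adds blocking by site. Neither uses RT status.

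**The concern.** Two patients with the same FACIT-F score at week 0 can be at different points of the expected course. On a six-week RT schedule, a patient randomised at the end of RT week 4 reaches the week 5 visit three weeks after RT (4 + 5 − 6). A patient randomised four weeks after RT reaches it at nine weeks (4 + 5). If recovery depends on time since RT, their expected changes differ whichever arm they are in.

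Late entrants are not a curiosity. In the Section 9 calendars for partial-breast and hypofractionated RT, the only FACIT scheduled after RT is at four weeks, so fatigue first detected there leads to randomisation at about four weeks or later.

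Three things are at stake: some precision in the primary estimate, its exposure to chance imbalance in RT status, and clarity. With no primary model named, a later decision to adjust the FACIT-F comparison for RT status would look post hoc, even though the plan already recognises the factor.

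**Working it through.** **1. Reproduce the plan's figure.** Section 12 gives: "Setting power as 0.8, and significance as 0.05, assuming a two-sided type I error, 122 patients per arm are required", for a difference in change "of at least 3.6 points on FACIT-fatigue", with scores distributed "with a standard deviation of 10 points". The unadjusted two-sample formula is

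n per arm = 2 × [(1.960 + 0.842) × 10 / 3.6]² = 121.1, rounded up to **122**.

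Power at 122 per arm is 0.803. The stated figure reproduces with no covariate, so the sample size gives RT status no role.

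**2. Assumptions.** The documents give neither the RT split nor the difference in recovery. Let p be the share in one RT group (assumed 0.3 to 0.5) and D the gap in mean FACIT-F change between the groups (assumed 4, 6 or 10 points). The value D = 10 is extreme: it equals the planning SD and the whole 10-point fall required for entry in Section 3.3.7.

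**3. Gain if the SD of 10 is the total SD.** RT status accounts for variance p(1 − p)D², so the adjusted SD is √(100 − p(1 − p)D²). The standard error is SD × √(2/122), and power is Φ(3.6/SE − 1.96).

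| D | p | p(1 − p)D² | Adjusted SD | Power |
|---|---|---|---|---|
| none | – | 0 | 10.00 | 0.803 |
| 4 | 0.3 | 3.36 | 9.83 | 0.816 |
| 4 | 0.5 | 4.00 | 9.80 | 0.819 |
| 6 | 0.3 | 7.56 | 9.61 | 0.833 |
| 6 | 0.5 | 9.00 | 9.54 | 0.838 |
| 10 | 0.3 | 21.0 | 8.89 | 0.886 |
| 10 | 0.5 | 25.0 | 8.66 | 0.901 |

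**4. Sensitivity: the SD of 10 is the SD within each RT group.** The unadjusted SD is then √(100 + p(1 − p)D²). Unadjusted power is about 0.79 at D = 4, 0.77 at D = 6 and 0.71–0.72 at D = 10. Adjustment restores 0.803.

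**5. Chance imbalance.** The 95% limit for the between-arm difference in RT share is 1.96 × √(2p(1 − p)/122), which is 11.5 percentage points at p = 0.3 and 12.5 at p = 0.5. Multiplied by D, the shift in the unadjusted difference is 0.46–0.50 points at D = 4, 0.69–0.75 at D = 6 and 1.15–1.25 at D = 10.

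This is not a second cost to add to step 3. With a total SD of 10, the unadjusted 95% half-width is 1.96 × 10 × √(2/122) = 2.51 points, and these shifts already lie within it. Steps 3 and 5 describe the same variance in two ways.

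**The case against.** **The covariate may already be meant for FACIT-F.** The plan has no separate section on analysis of the primary endpoint where the sentence could have gone, and Section 9 speaks of examining covariates of fatigue itself. This stands. A reader might infer that RT status was deliberately kept out of the primary analysis; the documents show only that no primary-analysis text includes it.

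**Nothing is biased.** This also stands for a comparison of all randomised patients: randomisation balances RT status on average. A reader might take the possible shifts as bias, which they are not. Sections 12.1 and 12.5.2 restrict the analysis to patients who complete the protocol, which weakens that protection if completion depends on arm and RT status. That is a problem of the analysis set, and a covariate does not by itself cure it.

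**The prognostic role is inferred.** Sections 2.1 and 2.2 describe a general course, and Section 2.3 allows persistence for weeks to months. Section 2.3 also puts onset at three to four weeks into RT, so on a six-week schedule typical entrants still on RT are two to three weeks past it by week 5. The contrast between groups may therefore be smaller than the extremes suggest. This supports calling RT status plausibly prognostic; the documents do not say that it drives recovery.

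**A drug effect lost in patients past RT.** In irradiated mice, "endorphin plasma levels diminish over the 4 weeks following the end of the radiation regimen", and a reader might infer that a benefit confined to patients on RT is being averaged away. That extrapolates from animal data, and a main-effect covariate would not recover such an effect.

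**RT dates.** The Clinical Variables form has no fields for first or last fraction, but that does not show the dates are uncollected. The monitoring calendar and the one-month entry window cannot be run without them.

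**Conclusion.** The point holds as a gap in specification with a modest gain in precision. RT status at randomisation is a plausible prognostic factor that the plan itself names, yet the primary comparison as written omits it. No stated figure is wrong: 122 per arm is correct for the unadjusted comparison.

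Under an assumed 30–50% split and a total SD of 10, including it moves power from about 80% to about 82% for a 4-point gap and 83–84% for 6 points. The figure of about 90% needs a 10-point gap and should not be taken as the expected benefit. These results rest on a split and a gap that the documents do not supply. What does not depend on them is that the change is nearly free and settles the choice before the data are seen.

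**What to change.** In Section 12.1, name the primary FACIT-F model and state that it includes RT status at week 0 (on RT or completed). The alternative is weeks from week 0 to the planned last fraction, with the actual date used only if RT was already complete. Either must be fixed at randomisation. In Section 12.4, say what the multivariate analysis is and which endpoints it covers.

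Do not use a last-fraction date that falls after randomisation. For patients still on RT that date is a post-randomisation variable, and Section 2.1 says severe fatigue can interrupt treatment, so study drug could affect it. Adjusting for it could introduce bias.

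The treatment effect by RT status may be reported as supportive only.

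The cost is a few sentences and one degree of freedom. Sample size, visits and randomisation are unchanged.

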12.5 Reporting and Exclusions

12.5.1 Evaluation of Toxicity

All participants will be evaluable for toxicity from the time of their first treatment. Some patients may tolerate the 25mg dose but develop toxicity after the dose is increased to 50mg. Hence, drug dose can be decreased from 50mg to 25mg in the setting of moderate to severe adverse events by CTCAE judged to be definitely or probably related to study drug.

Study drug (either at the 25mg or 50mg dose) can also be held for up to three days and then restarted in setting of moderate or severe adverse events by CTCAE if these events are judged to be possible, unlikely or unrelated to study drug. If the drug must be held for more than three days, the participant will need to come off the study.

12.5.2 Evaluation of Response

All of the participants who meet the eligibility criteria, consent to randomization, and complete the entire treatment protocol will be included in the main analysis of effect.

For all dropouts, we will use an off-study form in order to obtain information about the reasons for not completing the study. We will use this information for post-hoc analyses to lessen the chance of bias due to missing data.

5.	1	2	3	4	5
6.	1	2	3	4	5

Eyes:

7. eye irritation	1	2	3	4	5
8. swelling	1	2	3	4	5
9. blurred vision	1	2	3	4	5
10. double vision	1	2	3	4	5
11. poor vision	1	2	3	4	5
12. light bothering your eyes	1	2	3	4	5

Any other problems with your eyes (please specify):

13.	1	2	3	4	5
14.	1	2	3	4	5

Ears:

15. earache	1	2	3	4	5
16. discharge	1	2	3	4	5
17. trouble hearing	1	2	3	4	5
18. ringing or whistling or other noise in ears	1	2	3	4	5

Any other problems with your ears (please specify):

19.	1	2	3	4	5
20.	1	2	3	4	5-

Mouth and Teeth:

21. sores in your mouth	1	2	3	4	5
22. dry mouth	1	2	3	4	5
23. too much saliva	1	2	3	4	5
24. swollen or sore tongue	1	2	3	4	5
25. bleeding gums	1	2	3	4	5
26. dental problems	1	2	3	4	5

Any other problems with your mouth or teeth (please specify):

27.	1	2	3	4	5
28.	1	2	3	4	5

Nose and Throat:

29. nasal congestion	1	2	3	4	5
30. nose bleeds	1	2	3	4	5
31. sore throat	1	2	3	4	5
32. laryngitis	1	2	3	4	5
33. difficulty swallowing	1	2	3	4	5

Any other problems with your nose or throat (please specify):

34.	1	2	3	4	5
35.	1	2	3	4	5

Chest:

36. chest pain	1	2	3	4	5
37. shortness of breath	1	2	3	4	5
38. wheezing	1	2	3	4	5
39. coughing	1	2	3	4	5
40. breast or nipple pain or discharge	1	2	3	4	5
41. breast tenderness	1	2	3	4	5

Any other trouble with your chest (please specify):

42.	1	2	3	4	5
43.	1	2	3	4	5

Heart:

44. rapid heart rate	1	2	3	4	5
45. irregular heart beat	1	2	3	4	5

Any other trouble with your heart (please specify):

46.	1	2	3	4	5
47.	1	2	3	4	5

Stomach and Abdomen:

48. stomach / abdominal discomfort	1	2	3	4	5
49. nausea	1	2	3	4	5
50. vomiting	1	2	3	4	5
51. heartburn	1	2	3	4	5

SAFTEE (2)

Below is a list of complaints people sometimes have. Please read each and circle the number corresponding to how much you have been bothered by that problem in the past week:

1 = not at all 2 = a little bit 3 = moderately 4 = quite a bit 5 = extremely

Any other trouble with stomach or abdomen (please specify):

52.	1	2	3	4	5
53.	1	2	3	4	5

Bowel:

54. diarrhea	1	2	3	4	5
55. constipation	1	2	3	4	5
56. gas	1	2	3	4	5
57. change in color of stools	1	2	3	4	5
58. hemorrhoids	1	2	3	4	5
59. painful bowel movements	1	2	3	4	5

Any other changes in your bowel movements (please specify):

60.	1	2	3	4	5
61.	1	2	3	4	5

Appetite:

62. appetite increase	1	2	3	4	5
63. appetite decrease	1	2	3	4	5
64. weight gain	1	2	3	4	5
65. weight loss	1	2	3	4	5
66. bad taste or change in taste	1	2	3	4	5
67. increased thirst	1	2	3	4	5

Any other change in appetite (please specify):

68.	1	2	3	4	5
69.	1	2	3	4	5

Urination:

70. painful urination	1	2	3	4	5
71. burning sensation with urination	1	2	3	4	5
72. difficulty in starting to urinate	1	2	3	4	5
73. decrease in force of urinary stream	1	2	3	4	5

74. more frequent urination	1	2	3	4	5
75. change in color of urine	1	2	3	4	5

Any other problems with urination (please specify):

76.	1	2	3	4	5
77.	1	2	3	4	5

FEMALES:

78. menstrual irregularity	1	2	3	4	5
79. cramps	1	2	3	4	5
80. heavy bleeding	1	2	3	4	5
81. spotting	1	2	3	4	5
82. tension	1	2	3	4	5
83. hot flashes	1	2	3	4	5
84. lengthening of menstrual period	1	2	3	4	5
85. shortening of menstrual period	1	2	3	4	5

Any other problems with menstrual period (please specify):

86.	1	2	3	4	5
87.	1	2	3	4	5

Genital and Sexual Functioning:

88. discomfort in genitals	1	2	3	4	5
89. swelling of or discharge from genitals	1	2	3	4	5
90. decrease in interest in sex	1	2	3	4	5
91. increase in interest in sex	1	2	3	4	5
92. delayed orgasm or inability to reach orgasm	1	2	3	4	5

93. **MALES:** difficulty achieving or maintaining an erection

	1	2	3	4	5
--	---	---	---	---	---

Any other problems with genitals or sexual functioning (please specify):

94.	1	2	3	4	5
95.	1	2	3	4	5

PITTSBURG SLEEP QUALITY INDEX

INSTRUCTIONS:

The following questions related to your usual sleep habits during the past month only. Your answers should indicate the most accurate replay for the majority of days and nights in the past month. Please answer all questions.

1. During the past month, what time have you usually gone to bed at night?

BED TIME _____

2. During the past month, how long (in minutes) has it usually taken you to fall asleep each night?

NUMBER OF MINUTES _____

3. During the past month, what time have you usually gotten up in the morning?

GETTING UP TIME _____

4. During the past month, how many hours of actual sleep did you get at night? (This may be different than the number of hours you spent in bed.)

HOURS OF SLEEP PER NIGHT _____

For each of the remaining questions, check the one best response. Please answer all questions.

5. During the past month, how often have you had trouble sleeping because you...

- a) Cannot get to sleep within 30 minutes

Not during past month _____	Less than once a week _____	Once or twice a week _____	Three or more times a week _____
--------------------------------	--------------------------------	-------------------------------	-------------------------------------

- b) Wake up in the middle of the night or early morning

Not during past month _____	Less than once a week _____	Once or twice a week _____	Three or more times a week _____
--------------------------------	--------------------------------	-------------------------------	-------------------------------------

- c) Have to get up to use the bathroom

Not during past month _____	Less than once a week _____	Once or twice a week _____	Three or more times a week _____
--------------------------------	--------------------------------	-------------------------------	-------------------------------------

d) Cannot breathe comfortably

Not during past month _____	Less than once a week _____	Once or twice a week _____	Three or more times a week _____
--------------------------------	--------------------------------	-------------------------------	-------------------------------------

e) Cough or snore loudly

Not during past month _____	Less than once a week _____	Once or twice a week _____	Three or more times a week _____
--------------------------------	--------------------------------	-------------------------------	-------------------------------------

f) Feel too cold

Not during past month _____	Less than once a week _____	Once or twice a week _____	Three or more times a week _____
--------------------------------	--------------------------------	-------------------------------	-------------------------------------

g) Feel too hot

Not during past month _____	Less than once a week _____	Once or twice a week _____	Three or more times a week _____
--------------------------------	--------------------------------	-------------------------------	-------------------------------------

h) Had bad dreams

Not during past month _____	Less than once a week _____	Once or twice a week _____	Three or more times a week _____
--------------------------------	--------------------------------	-------------------------------	-------------------------------------

i) Have pain

Not during past month _____	Less than once a week _____	Once or twice a week _____	Three or more times a week _____
--------------------------------	--------------------------------	-------------------------------	-------------------------------------

j) Other reason(s), please describe _____

Not during past month _____	Less than once a week _____	Once or twice a week _____	Three or more times a week _____
--------------------------------	--------------------------------	-------------------------------	-------------------------------------

6. During the past month, how would you rate your sleep quality overall?

Very good _____

Fairly good _____

Fairly bad _____

Very bad _____

7. During the past month, how often have you taken medicine to help you sleep (prescribed or “over the counter”)?

Not during past month _____ Less than once a week _____ Once or twice a week _____ Three or more times a week _____

8. During the past month, how often have you had trouble staying awake while driving, eating meals, or engaging in social activity?

Not during past month _____ Less than once a week _____ Once or twice a week _____ Three or more times a week _____

9. During the past month, how much of a problem has it been for you to keep up enough enthusiasm to get things done?

No problem at all _____
Only a very slight problem _____
Somewhat of a problem _____
Very bad _____

Patient Initials/Signature: _____

Date: _____

Patient ID: _____

Date: _____

Visit#: _____

PHQ-9 — Nine Symptom Checklist

1. Over the last 2 weeks, how often have you been bothered by any of the following problems? Read each item carefully, and circle your response.

a. Little interest or pleasure in doing things

Not at all Several days More than half the days Nearly every day

b. Feeling down, depressed, or hopeless

Not at all Several days More than half the days Nearly every day

c. Trouble falling asleep, staying asleep, or sleeping too much

Not at all Several days More than half the days Nearly every day

d. Feeling tired or having little energy

Not at all Several days More than half the days Nearly every day

e. Poor appetite or overeating

Not at all Several days More than half the days Nearly every day

f. Feeling bad about yourself, feeling that you are a failure, or feeling that you have let yourself or your family down

Not at all Several days More than half the days Nearly every day

g. Trouble concentrating on things such as reading the newspaper or watching television

Not at all Several days More than half the days Nearly every day

h. Moving or speaking so slowly that other people could have noticed. Or being so fidgety or restless that you have been moving around a lot more than usual

Not at all Several days More than half the days Nearly every day

i. Thinking that you would be better off dead or that you want to hurt yourself in some way

Not at all Several days More than half the days Nearly every day

2. If you checked off any problem on this questionnaire so far, how difficult have these problems made it for you to do your work, take care of things at home, or get along with other people?

Not Difficult at all Somewhat Difficult Very Difficult Extremely Difficult

Patient Initials/Signature: _____

Date: _____

Patient ID: _____

Date: _____

Visit #: _____

PATIENT GLOBAL IMPRESSIONS: SEVERITY OF FATIGUE

Targum and Fava © Massachusetts General Hospital

Symptoms of fatigue may include effects on:

Your physical wellbeing:

Low or decreased energy, tiredness, decreased physical endurance or ability to sustain physical activity, general weakness, heaviness in the arms or legs, general heaviness, slowness or sluggishness, sleepiness, increased effort with physical tasks.

Your mood state:

Decreased motivation or interest, decreased effort or initiative.

Your cognitive abilities:

Decreased concentration, decreased attention, slowed thinking, reduced mental sharpness.

Within the past week, how troublesome (disturbing or distressing) have the identified symptoms of fatigue been for you?

CIRCLE THE NUMBER CORRESPONDING TO YOUR RATING

1	Normal, no symptoms of fatigue	No symptoms of fatigue have been present in the past seven days
2	Borderline symptoms	There may have been subtle symptoms of fatigue but there was no meaningful impact on your behavior or function
3	Mild fatigue	There have been some clear symptoms of fatigue but they may have cause minimal, if any, emotional distress or difficulty for you in social or occupational situations
4	Moderate fatigue	There have been overt (definite) symptoms of fatigue causing noticeable, but modest, functional difficulties (impairment) or distress for you; These symptoms are interfering with (but not

		stopping) social, educational, or occupational function
5	Marked fatigue	There have been intrusive symptoms of fatigue that distinctly impair social or occupational activities or function and/or cause high levels of distress; The functional interference due to these symptoms is obvious to others
6	Severe fatigue	The symptoms of fatigue are very distressing to you and are disrupting behavior or function in multiple domains of function (social, occupation, school)
7	Extreme fatigue	Symptoms of fatigue are drastically interfering in many life functions; You may be unable to work or attend school

Patient Initials/Signature: _____

Date: _____

Patient ID: _____

Date: _____

Visit #: _____

PATIENT GLOBAL IMPRESSIONS–IMPROVEMENT

Targum and Fava © Massachusetts General Hospital

Rate total improvement of fatigue within the past week whether or not it is due entirely to drug treatment

Compared to how you felt previously, how much have you changed over the past week?

CIRCLE THE NUMBER CORRESPONDING TO YOUR RATING

1	Very much improved	Nearly all better ; good level of functioning; Minimal symptoms of fatigue if any at all; This level represents a very substantial change from the baseline assessment
2	Much improved	Notably better with significant reduction of symptoms; Increase in the level of functioning but some symptoms of fatigue may remain
3	Minimally improved	Slightly better ; There may be only a modest change in symptoms of fatigue or functional capacity
4	No change	Symptoms of fatigue remain essentially unchanged
5	Minimally worse	Slightly worse but may not be clinically meaningful; There may be only a modest worsening of symptoms or functioning
6	Much worse	Notably worse with significant increase of symptoms of fatigue; Associated decrease in the level of functioning
7	Very much worse	Severe exacerbation of symptoms and profound impact on behavior and/or functioning

Patient Initials/Signature: _____

Date: _____

Patient ID: _____

Date: _____

Visit #: _____

Table 1. Massachusetts General Hospital CPFQ

(a) How has your motivation/interest/enthusiasm been over the past month?					
1	2	3	4	5	6
greater than normal	normal	minimally diminished	moderately diminished	markedly diminished	totally absent
(b) How has your wakefulness/alertness been over the past month?					
1	2	3	4	5	6
greater than normal	normal	minimally diminished	moderately diminished	markedly diminished	totally absent
(c) How has your energy been over the past month?					
1	2	3	4	5	6
greater than normal	normal	minimally diminished	moderately diminished	markedly diminished	totally absent
(d) How has your ability to focus/sustain attention been over the past month?					
1	2	3	4	5	6
greater than normal	normal	minimally diminished	moderately diminished	markedly diminished	totally absent
(e) How has your ability to remember/recall information been over the past month?					
1	2	3	4	5	6
greater than normal	normal	minimally diminished	moderately diminished	markedly diminished	totally absent
(f) How has your ability to find words been over the past month?					
1	2	3	4	5	6
greater than normal	normal	minimally diminished	moderately diminished	markedly diminished	totally absent
(g) How has your sharpness/mental acuity been over the past month?					
1	2	3	4	5	6
greater than normal	normal	minimally diminished	moderately diminished	markedly diminished	totally absent

Please answer all questions by *circling* the correct answer or the answer which seems the most *appropriate* to you (consider 'normal' the time in your life prior to the past month when you were most satisfied with your cognitive and physical functioning). Copyright: Massachusetts General Hospital.

Patient Initials/Signature: _____

Date: _____

Patient ID: _____

Date: _____

Visit#: _____

Insomnia Severity Index

For each question, please CIRCLE the number that best describes your answer.

Please rate the CURRENT (i.e. LAST 2 WEEKS) SEVERITY of your insomnia problem(s).

Insomnia Problem	None	Mild	Moderate	Severe	Very Severe
1. Difficulty falling asleep	0	1	2	3	4
2. Difficulty staying asleep	0	1	2	3	4
3. Problems waking up too early	0	1	2	3	4

4. How SATISFIED/DISSATISFIED are you with your CURRENT sleep pattern?

Very Satisfied Satisfied Moderately Satisfied Dissatisfied Very Dissatisfied
0 1 2 3 4

5. How NOTICEABLE to others do you think your sleep problem is in terms of impairing the quality of your life?

Not at all
Noticeable A Little Somewhat Much Very Much Noticeable
0 1 2 3 4

6. How WORRIED/DISTRESSED are you about your current sleep problem?

Not at all
Worried A Little Somewhat Much Very Much Worried
0 1 2 3 4

7. To what extent do you consider your sleep problem to INTERFERE with your daily functioning (e.g. daytime fatigue, mood, ability to function at work/daily chores, concentration, memory, mood, etc.) CURRENTLY?

Not at all
Interfering A Little Somewhat Much Very Much Interfering
0 1 2 3 4

Patient Initials/Signature: _____

Date: _____

Generalized Anxiety Disorder – 7 questions

Instructions: for each question below, please circle the number of the statement that best matches how you feel

How often during the past 2 weeks have you felt bothered by:

1. Feeling nervous, anxious, or on edge?

- 0 = not at all
- 1 = several days
- 2 = more than half the days
- 3 = nearly everyday

2. Not being able to stop or control worrying?

- 0 = not at all
- 1 = several days
- 2 = more than half the days
- 3 = nearly everyday

3. Worrying too much about different things?

- 0 = not at all
- 1 = several days
- 2 = more than half the days
- 3 = nearly everyday

4. Trouble relaxing?

- 0 = not at all
- 1 = several days
- 2 = more than half the days
- 3 = nearly everyday

5. Being so restless that it is hard to sit still?

- 0 = not at all
- 1 = several days
- 2 = more than half the days
- 3 = nearly everyday

6. Becoming easily annoyed or irritable?

- 0 = not at all
- 1 = several days
- 2 = more than half the days
- 3 = nearly everyday

7. Feeling afraid as if something awful might happen?

- 0 = not at all
- 1 = several days
- 2 = more than half the days
- 3 = nearly everyday

If you checked off any problems, how difficult have these problems made it for you to do your work, take care of things at home, or get along with other people?

(Please circle one option below)

- Not difficult at all
- Somewhat difficult
- Very difficult
- Extremely difficult

Patient Initials/Signature: _____

Date: _____

Functional Assessment of Chronic Illness Therapy (FACIT) Fatigue Scale (Version 4)

Below is a list of statements that other people with your illness have said are important. Please circle or mark one number per line to indicate your response as it applies to the past 7 days.

		Not At All	A Little Bit	Somewhat	Quite a Bit	Very Much
1	I feel fatigued	0	1	2	3	4
2	I feel weak all over	0	1	2	3	4
3	I feel listless ("washed out")	0	1	2	3	4
4	I feel tired	0	1	2	3	4
5	I have trouble starting things because I am tired	0	1	2	3	4
6	I have trouble finishing things because I am tired	0	1	2	3	4
7	I have energy	0	1	2	3	4
8	I am able to do my usual activities	0	1	2	3	4
9	I need to sleep during the day	0	1	2	3	4
10	I am too tired to eat	0	1	2	3	4
11	I need help doing my usual activities	0	1	2	3	4
12	I am frustrated by being too tired to do the things I want to do	0	1	2	3	4
13	I have to limit my social activity because I am tired	0	1	2	3	4

Scoring: Items are scored as follows: 4=Not At All; 3=A Little Bit; 2=Somewhat; 1=Quite A Bit; 0=Very Much, EXCEPT items #7 and #8 which are reversed scored. Score range 0-52. A score of less than 30 indicates severe fatigue. The higher the score, the better the quality of life.

Item Number	Reverse Item?		Item Response	Item Score
1	4	-		=
2	4	-		=
3	4	-		=
4	4	-		=
5	4	-		=
6	4	-		=
7	0	+		=
8	0	+		=
9	4	-		=
10	4	-		=
11	4	-		=
12	4	-		=
13	4	-		=

Sum individual item scores: _____
 Multiply by 13: _____
 Divide by number of items answered: _____

For guidelines on handling missing data and scoring options, please refer to the Administration and Scoring Guidelines on-line at www.facit.org.

Source: Webster, K., Cella, D., & Yost, K. (2003). The functional assessment of chronic illness therapy (FACIT) measurement system: properties, applications and interpretation. *Health and Quality of Life Outcomes*, 1(79), 1-7.

Reprinted with permission from: <http://www.facit.org/FACITOrg/Questionnaires>

Best Practices in Nursing
Can't Do It? We'll Help!

A series provided by The Hartford Institute for Geriatric Nursing,
New York University, College of Nursing

EMAIL: [contact] | HARTFORD INSTITUTE WEBSITE: www.hartfordign.org
 CLINICAL NURSING WEBSITE: www.ConsultGerRN.org

Patient ID: _____

Date: _____

Visit#: _____

FACT-B (Version 4)

Below is a list of statements that other people with your illness have said are important. **Please circle or mark one number per line to indicate your response as it applies to the past 7 days.**

PHYSICAL WELL-BEING		Not at all	A little bit	Some- what	Quite a bit	Very much
GP1	I have a lack of energy	0	1	2	3	4
GP2	I have nausea	0	1	2	3	4
GP3	Because of my physical condition, I have trouble meeting the needs of my family	0	1	2	3	4
GP4	I have pain	0	1	2	3	4
GP5	I am bothered by side effects of treatment	0	1	2	3	4
GP6	I feel ill	0	1	2	3	4
GP7	I am forced to spend time in bed	0	1	2	3	4

SOCIAL/FAMILY WELL-BEING		Not at all	A little bit	Some- what	Quite a bit	Very much
GS1	I feel close to my friends	0	1	2	3	4
GS2	I get emotional support from my family	0	1	2	3	4
GS3	I get support from my friends.....	0	1	2	3	4
GS4	My family has accepted my illness	0	1	2	3	4
GS5	I am satisfied with family communication about my illness.....	0	1	2	3	4
GS6	I feel close to my partner (or the person who is my main support)	0	1	2	3	4
Q1	Regardless of your current level of sexual activity, please answer the following question. If you prefer not to answer it, please mark this box  and go to the next section.					
GS7	I am satisfied with my sex life	0	1	2	3	4

Patient ID: _____

Date: _____

Visit#: _____

FACT-B (Version 4)

Please circle or mark one number per line to indicate your response as it applies to the past 7 days.

EMOTIONAL WELL-BEING

		Not at all	A little bit	Some- what	Quite a bit	Very much
GE1	I feel sad	0	1	2	3	4
GE2	I am satisfied with how I am coping with my illness.....	0	1	2	3	4
